5.1 Assignment of Treatment

All patients will receive CPX-351 with quizartinib according to the treatment plan (Section 5.2).

5.2 Treatment Plan

The plan for administration is divided into three phases: induction, consolidation, and maintenance. In patients who decline HCT or cellular therapy (CT) intervention or are ineligible, the patient would proceed through induction, consolidation, and maintenance.

Patients who achieve a CR (CR or CRi) after induction(s), will proceed to consolidation followed by the maintenance phase. In patients who achieve a PR, re-induction can occur for one additional cycle followed by consolidation and maintenance phases if a CR is achieved with re-induction. In patients who achieve a CR or PR after induction and/or consolidation and an HCT or other CT intervention (e.g., HCT or DLI) is indicated, maintenance therapy would be initiated no earlier than Day 30 after the HCT or CT intervention. If the patient is on quizartinib prior to HCT or CT intervention, quizartinib should be discontinued 7 days prior if a conditioning therapy is utilized. If proceeding to a CT intervention without conditioning therapy (e.g., DLI), quizartinib should be discontinued one day prior to CT intervention.

Response assessment will occur by BM biopsy/aspirate 21 days (± 2 days) from CPX-351 induction and/or re-induction therapy as well as Day 35 (± 7 days) during induction and consolidation therapy (within 4 days after neutrophil as defined as a peripheral ANC $\geq 500/\mu\text{L}$ for 24 hours). In the event of a delayed neutrophil recovery, defined as having a peripheral ANC $< 500/\mu\text{L}$ at Day 42 from the first day of CPX-351 treatment, a BM biopsy will be taken to assess persistent disease. During the maintenance phase, subsequent response assessments by BM biopsy/aspirate will be done on Day 24 (± 3 days) of a 28-day treatment cycle during Cycles 3, 6, 12, and 24.

5.2.1 Treatment Location

5.2.1.1 Inpatient procedures

Patients will be admitted to the clinic as inpatients to start induction therapy. If the Day +21 (± 2 days) BM aspirate shows no evidence of disease, the patient is stable based on PI assessment, and close outpatient follow-up is available, then the patient can be discharged with three weekly lab checks (Monday, Wednesday, and Friday) and weekly provider visits.

5.2.1.2 Outpatient procedures

Consolidation cycles may be administered on an outpatient basis with IV infusion of CPX-351 and three weekly lab checks (Monday, Wednesday, and Friday) and weekly provider visits. Maintenance cycles are all outpatient with monthly lab/provider visits.

5.2.2 Induction Phase

Treatment consists of CPX-351 (liposomal daunorubicin $44 \text{ mg}/\text{m}^2$ IV and cytarabine $100 \text{ mg}/\text{m}^2$ IV) on Days 1, 3, and 5 followed by quizartinib (30 mg by mouth [PO] once daily) on Days 8-21. If there is a PR at the recovery BM biopsy, patients may be re-treated with one additional induction therapy (re-induction) with CPX-351 (daunorubicin $44 \text{ mg}/\text{m}^2$ IV and cytarabine 100

CONFIDENTIAL

mg/m² IV) on Days 1 and 3. Quizartinib (30 mg by PO once daily) will resume on Day 6 and continue through Day 21. If re-induction is required, a minimum 72-hour period is necessary between the dose of quizartinib on Day 21 and the administration of CPX-351 with re-induction.

If it is believed by the PI and/or sub-investigator that a patient with prolonged Grade ≥ 3 toxicity after the induction phase would be likely to experience additional toxicities during the consolidation phase, the patient could bypass the consolidation phase and proceed to a cellular intervention or the maintenance phase. Any patient with neutropenia or thrombocytopenia lasting ≥ 56 days from the initiation of CPX-351 will not receive consolidation and will instead proceed to the maintenance phase.

5.2.3 Consolidation Phase

Patients who achieve a CR and do not proceed to an alloHCT or other CT intervention will proceed from induction to the consolidation phase beginning 7 days (± 7 days) after neutrophil recovery (ANC $> 1000/\mu\text{L}$), receiving up to 2 consolidation cycles consisting of CPX-351 (daunorubicin 29 mg/m² IV and cytarabine 65 mg/m² IV) on Days 1 and 3. Quizartinib therapy (30 mg PO once daily) will start on Day 6 and continue through Day 21.

After the first consolidation cycle, if it is believed by the PI and/or sub-investigator that a patient with prolonged Grade ≥ 3 toxicity would have additional adverse toxicities during the second consolidation phase, and/or there is CRi with persistent ANC $< 1000/\mu\text{L}$ and/or platelets $< 50,000/\mu\text{L}$ more than 14 days from the recovery marrow assessment, then the patient could proceed to a cellular intervention or the maintenance phase.

5.2.4 Maintenance Phase

The maintenance phase consists of 28-day cycles. Patients will receive quizartinib once daily for a total of 24 cycles or until disease relapse. Maintenance dosing of quizartinib will begin at 30 mg PO once daily on Days 1-14, and if there are no non-hematologic Grade ≥ 3 toxicities and QTcF is maintained ≤ 450 msec, the quizartinib dose will increase to 60 mg/day on Day 15. If consolidation therapy is not advised at all or if only 1 cycle of consolidation is advised based on prolonged toxicities, maintenance therapy will begin 7 days (± 7) after neutrophil recovery (ANC $> 1000/\mu\text{L}$) from the consolidation phase or induction phase.

Patients who proceed to alloHCT or other CT intervention after consolidation will resume quizartinib maintenance no earlier than Day 30 from the intervention or transplant. If ≥ 2 CT interventions (e.g., repeat DLI) are planned after maintenance, a 28-day hold is acceptable, with resumption of quizartinib with the next cycle. If the patient is on quizartinib prior to HCT or CT intervention, quizartinib should be discontinued 7 days prior if a conditioning therapy is utilized. If proceeding to a CT intervention without conditioning therapy (e.g., DLI), quizartinib should be discontinued one day prior to CT intervention.

5.3 Concomitant Medications

Patients will be instructed not to take any additional medications during the course of the study without prior consultation with the research team. At each visit, the patient will be asked about any new medications he/she is taking or has taken after the start of the study drug.

CONFIDENTIAL

STUDY DRUG: QUIZARTINIB
PROTOCOL DATE: 10 AUGUST 2020

DEVELOPMENT INNOVATIONS STUDY NUMBER: AML 48
VERSION 4.0

5.3.1 Permitted Concomitant Medications

Patients with hematologic malignancies receiving therapy are at an increased risk for infections, and antiviral, antifungal, and antibacterial prophylactic agents should be administered per institutional guidelines. It is considered routine practice to administer acyclovir or a similar antiviral to reduce the risk of herpes simplex virus (HSV) or varicella zoster virus (VZV) reactivation, voriconazole or other anti-fungal agent to reduce the risk of a fungal infection, and an antibiotic such as levofloxacin to reduce the risk of neutropenic fever. It is important to note that many antifungal agents require a dose modification of quizartinib. Electrocardiograms (ECGs) will need to be performed on patients who receive medications that cause significant QTc prolongation.

Additional supportive care measures (e.g., anti-emetics for nausea, anti-motility agents for diarrhea management) are permitted at the Investigator's discretion. Concomitant treatments and/or procedures that are required to manage a patient's medical condition during the study will be recorded in the electronic case report form (eCRF).

5.3.2 Prohibited Concomitant Medications

The following treatments are prohibited during the treatment period of the study:

- Other investigational therapies (e.g., chemotherapy, radiation therapy, surgery, immunotherapy, biologic therapy, or hormonal therapy not required by this protocol) should not be given to patients. If such agents are required for a patient, then the patient must first be withdrawn from the study.
- Herbal preparations/medications are not allowed throughout the study unless approved by the Investigator. Herbal medications include, but are not limited to: St. John's wort, kava, ephedra (ma huang), ginkgo biloba, dehydroepiandrosterone (DHEA), yohimbe, saw palmetto, and ginseng. Patients should stop using herbal medications 7 days prior to first dose of study drug.
- While receiving quizartinib, concomitant medications that prolong the QT/QTc interval are prohibited except when regarded by the Investigator as essential for patient care (Appendix F and Appendix I).
- Strong CYP3A4 inhibitors are not prohibited, although quizartinib dose adjustments are required. Weak or moderate CYP3A4 inhibitors, such as fluconazole, may be used without dose reduction (Appendix H).
 - When treatment with a strong CYP3A4 inhibitor is initiated, reduce quizartinib one dose level (60 mg to 30 mg or 30 mg to 20 mg)
 - A patient taking a strong CYP3A4 inhibitor at enrollment will begin quizartinib treatment at 20 mg/day. The dose will be escalated to 30 mg/day at Day 15 of the maintenance phase if the QTcF interval is ≤ 450 msec prior to or at the Day 14 ECG evaluation.
- Concomitant strong or moderate CYP3A4 inducers are prohibited (Appendix H).
- Concomitant agents that prolong QTc are prohibited (Appendix I)

CONFIDENTIAL

If quizartinib is co-administered with drugs that inhibit P-glycoprotein (P-gp) or are substrates of P-gp, increased concentrations of quizartinib are possible and caution should be exercised. The co-administration of P-gp inhibitors and inducers with quizartinib should be avoided if possible.

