3.3 Discontinuation from Study Treatment

Patients will be discontinued from study treatment for any of the following reasons:

- Irreversible or intolerable toxicity or abnormal laboratory values thought to be related to drug toxicity
- Conditions requiring therapeutic intervention not permitted by the protocol
- Intercurrent illness (this will be at the Investigator's discretion)
- Inability of the patient to comply with study requirements
- Patient requests to discontinue treatment, but agrees to finish study procedures
- Patient withdraws consent from the study and is discontinued from the study
- Non-compliance/lost to follow-up
- Pregnancy and breastfeeding
- Further participation would be injurious to the patient's health or well-being, in the Investigator's medical judgment

CONFIDENTIAL

STUDY DRUG: QUIZARTINIB
 PROTOCOL DATE: 10 AUGUST 2020

DEVELOPMENT INNOVATIONS STUDY NUMBER: AML 48
 VERSION 4.0

- The study is terminated by the Sponsor, Sarah Cannon Development Innovations (“Development Innovations”) or the Institutional Review Board (IRB)

After discontinuation from protocol treatment, patients must be followed for adverse events (AEs) for 30 days after their last dose of study drug. All new AEs occurring during this period must be reported and followed at the site until resolution for AEs attributed to the study medication(s).

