5. STUDY DESIGN

This is a multi-center, non-randomized, open-label, two-part prospective Phase II clinical trial in patients with relapsed or refractory FLT3-ITD mutation-positive AML. The study is designed to assess the safety and tolerability as well as the efficacy of administering CPX-351 (cytarabine:daunorubicin liposome complex) with quizartinib, a second-generation FLT3 inhibitor. The plan for administration is divided into three phases: induction, consolidation, and maintenance. Approximately 34 patients are planned to be screened and enrolled. Patient participation is expected to be 4 years.

A total of 10 patients will be enrolled in the safety lead-in. The safety lead-in portion of the study is designated as Part 1. If >3 patients experience delayed neutrophil count recovery >56 days from the first day on the study regimen, or delayed thrombocytopenia recovery >56 days from the first day on the study regimen, or if >3 patients develop a non-hematologic toxicity, defined as a Grade 4 non-hematologic adverse event determined to be probably related to the combined treatment, or a Grade 4 neutropenia, then the study will be terminated.

Assuming safety parameters are met, the first 10 patients will be followed for response in the Part 2 of the study. An additional 24 patients will be enrolled in Part 2 of the study (induction, consolidation and maintenance). All patients will be assessed for response.

Patients who fail to respond to therapy will be followed until a new therapy is instituted. . Patients who experience an AE that results in the discontinuation of study treatment will be

[figure not shown]
CONFIDENTIAL

STUDY DRUG: QUIZARTINIB
PROTOCOL DATE: 10 AUGUST 2020

DEVELOPMENT INNOVATIONS STUDY NUMBER: AML 48
VERSION 4.0

followed until resolution/stabilization for AEs attributed to the medication. Outcomes for all patients will be assessed for 24 months from the date of last treatment.

Figure 1 Study Schema

*All treatment phases follow a 28-day cycle. Induction and re-induction consist of: CPX-351 (liposomal daunorubicin 44 mg/m² IV and cytarabine 100 mg/m² IV) + quizartinib 30 mg PO QD. The maintenance phase: begin quizartinib 30 mg PO QD on Days 1-14. If there are no toxicities and QTcF is maintained ≤ 450 msec, increase dose to 60 mg QD on Day 15.

[†]For one cycle

[‡]For up to two cycles

CONFIDENTIAL

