6.4.5 End of Treatment/Early Termination Visit

Patients will complete the study at the time of PD, if they withdraw consent, if they withdraw due to an AE, or at the time the study is terminated. If either study treatment or patients are discontinued, the reason will be recorded in the eCRF and source document. Patients who are removed from treatment for reasons other than death or disease progression (PD) are considered to be patients who have terminated early. Reasons for discontinuation include one of the following: AEs, protocol violation, patient withdraws consent, patient is lost to follow-up, administrative reasons (including study closure), death, or other. Patients who complete or discontinue from the study should have the following study completion/early withdrawal evaluations performed as soon as possible after the day of study completion/early withdrawal.

- Physical examination and vital signs

CONFIDENTIAL

STUDY DRUG: QUIZARTINIB
 PROTOCOL DATE: 10 AUGUST 2020

DEVELOPMENT INNOVATIONS STUDY NUMBER: AML 48
 VERSION 4.0

- ECOG performance status
- AE monitoring
- Concomitant medication review
- CBC and clinical chemistry panels
- BM biopsy and aspirate with FLT3 mutation testing, if applicable
- ECG and QTcF assessment, if applicable

Patients prematurely discontinuing from the study must be followed for AE and concomitant medication use for 30 days following the last administration of study drugs or until resolution/stabilization of an ongoing AE attributed to the medication.

Patients who discontinue from the study may be treated with other therapies at the discretion of the Investigator.

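### Two sentences (Sections 5.3.2 and 5) can be read as ending follow-up when other therapy starts, against the 24-month survival follow-up planned for all patients

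*Combined protocol and SAP*

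**What the plan says.** Two sentences tie the start of other therapy to the end of participation or follow-up.

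- Section 5.3.2, in the item on other investigational therapies: "If such agents are required for a patient, then the patient must first be withdrawn from the study". The section applies during the treatment period. The examples in that item are broad and include chemotherapy, radiation and immunotherapy that the protocol does not require.
- Section 5: "Patients who fail to respond to therapy will be followed until a new therapy is instituted".

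Other sections point the other way.

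- Section 3.3 opens its list with "Patients will be discontinued from study treatment for any of the following reasons", and one listed reason is "Conditions requiring therapeutic intervention not permitted by the protocol". Within that list, only the consent-withdrawal item says in terms that the patient is discontinued from the study.
- Section 5, two sentences after the non-responder sentence: "Outcomes for all patients will be assessed for 24 months from the date of last treatment".
- Section 6.4.6 and Appendix D footnote m schedule disease assessment and survival status every 6 months for 2 years after study treatment. Neither makes an exception for patients who start something new.

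Section 9.9 defines OS as time to death from any cause. Patients not known to have died are censored when last known alive or last contacted. Section 10.4.2 reports Kaplan-Meier OS rates at 6, 12 and 24 months.

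**The concern.** A site that applies either sentence as written could stop collecting vital status when a patient moves to other therapy. Section 9.9 would then censor that patient at about that time. Kaplan-Meier estimation assumes that censored patients have the same later risk as those still followed. Starting a new therapy, above all after non-response, is related to prognosis, so the assumption would be doubtful. If the censored patients do worse than those who remain, the OS rates come out too high. Sites could also differ in which sentence they follow, and the analysis could not tell this apart from ordinary loss to follow-up.

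**Working it through.** **Design figure.** The only calculated figure in the plan is the response-rate design in Section 10.2: null 27%, alternative 50%, reject with 13 or more responses in 30. Exact binomial calculation gives:

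- P(X ≥ 13 | n = 30, p = 0.27) = 0.0395, below the 0.05 target;
- P(X ≥ 13 | n = 30, p = 0.50) = 0.819, consistent with the stated 80%;
- 30 / (1 − 0.10) = 33.3, rounded up to 34 enrolled.

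The design reproduces, and nothing in it depends on the wording at issue. Response is measured at the marrow assessments (Section 5.2: "Response assessment will occur by BM biopsy/aspirate 21 days", and again around Day 35), and Section 10.4.2 takes it at the recovery assessment. Both readings stop study treatment. They differ only in what is collected afterwards.

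**The texts side by side.**

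| Situation | Text that ends participation or follow-up | Text that continues it |
|---|---|---|
| Needs therapy the protocol does not allow | 5.3.2: withdrawal from the study | 3.3: study treatment stops; 6.4.6 and footnote m: 2 years of follow-up |
| Non-responder starts new therapy | 5: followed up to that point | 5: outcomes for all patients for 24 months; 6.4.6 and footnote m |

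No sentence says that survival follow-up continues after a withdrawal under 5.3.2, or once a new therapy has started. A site looking up its duties to such a patient would find this in Section 6.4.5: "Patients prematurely discontinuing from the study must be followed for AE and concomitant medication use for 30 days following the last administration", extended for an ongoing attributed adverse event. Survival is not mentioned there.

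**What a literal reading removes, per affected patient.** Follow-up lasts 24 months with a visit every 6 months: 24 / 6 = 4 visits, each with disease status and survival status. Up to 4 are lost.

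**Which endpoints are exposed.** OS is exposed, as is late disease status. Section 9.7 already excludes long-term follow-up data from event-free survival, so the loss of those visits does not change that endpoint.

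**The case against.** The strongest reply is that the protocol uses leaving the study loosely and plainly means to keep following patients.

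- Section 6.4.5 says "Patients will complete the study at the time of PD", yet survival follow-up comes after that. It also allows other therapies after a patient discontinues from the study, and Section 6.4.6 follows directly with survival visits.
- Section 11.3.4 provides for deaths during survival follow-up after the study, with its own case report form screen.
- Section 13.3.1.1 asks sites to seek permission for vital status even from patients who revoke authorization to use their health information.
- In Section 5 the non-responder sentence and the adverse-event sentence after it can be read as rules for particular groups, with the all-patients sentence as the general rule.
- Section 5.3.2 is confined to the treatment period and to other investigational therapies, and the Section 5 sentence to non-responders. Neither reaches every patient who starts something new.

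Most of this stands. It makes continued follow-up the likely intent, and it limits the scope. It does not remove the conflict. The Section 11.3.4 wording concerns deaths attributed to progression, whereas treatment failure in Section 9.4 is anything less than a partial response. The Section 5 paragraph does not say which sentence governs.

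Three stronger readings are tempting, and the documents do not support them.

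- A reader might infer that OS data will be lost. The sections above point the other way, so this is a risk from wording.
- A reader might date the last contact by adding 30 days of adverse-event follow-up to the last induction dose of quizartinib on Day 21, giving Day 51, well before the 6-month OS estimate. That assumes new therapy has started by then. Section 5 keeps a non-responder in follow-up until it starts, and no document gives that date.
- A reader might take all patients without CR or CRi as affected: 34 × (1 − 0.50) = 17 to 34 × (1 − 0.27) = 24.8, so about 17 to 25. Some of these would be partial responses, not all would start another therapy, and not every site would read the text literally.

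**Conclusion.** The conflict in wording is real and should be corrected. Its reach is limited to OS, a secondary endpoint with no planned test, and to late disease status. If a site reads either sentence literally, an affected patient loses up to 4 follow-up visits and is censored for OS at a time related to prognosis. This rests on two assumptions: that some sites would follow the narrower sentence, and that patients who start other therapy differ in prognosis from those who do not. The size of any bias cannot be estimated. The documents do not give the number of patients affected, when they would start new therapy, their later survival, or how sites would read the text. The response-rate test, sample size and power stand as planned.

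**What to change.** In Section 5.3.2, replace withdrawal from the study with: *discontinued from study treatment (Section 3.3); disease-status and survival follow-up under Section 6.4.6 continues unless consent is withdrawn.*

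In Section 5, replace the non-responder sentence with: *Non-responders have on-study response assessments until a new therapy starts; disease-status and survival follow-up under Section 6.4.6 continues for 24 months after last treatment, whether or not a new therapy starts, unless consent is withdrawn.*

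The cost is two sentences in an amendment. No visits, procedures or data items are added, because Sections 5 and 6.4.6 and Appendix D footnote m already plan this follow-up.

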6. STUDY ASSESSMENTS AND EVALUATIONS

6.1 Overview

All patients should visit the study center on the days specified within this protocol. The complete Schedule of Assessments for this study is presented in Appendix D.

6.2 Baseline Study Assessments

The following information will be collected and procedures will be performed for each patient at a baseline study assessment. This screening assessment will take place following written informed consent (see Section 13.3) and within 7 days prior to initiating study treatment.

- Medical history and demographics
- Physical examination (including height [screening only] and weight)
- Vital signs (pulse, resting blood pressure, respiratory rate, and body temperature)
- ECOG performance status (Appendix A)
- 12-lead ECG need to be completed pre-dose and 5 minutes apart, if QTcF prolongation is identified assess electrolyte levels (including potassium and magnesium) as clinically indicated.
- Concomitant medication review
- Complete blood count (CBC) including differential count
- Chemistry panel: sodium (Na), potassium (K), phosphorus (PO₄), chloride (Cl), Cr, calcium (Ca), bicarbonate (CO₂), AST, ALT, alkaline phosphatase (ALP), total bilirubin, lactate dehydrogenase (LDH), uric acid, glucose, and blood urea nitrogen (BUN)
- Urinalysis
- Serum pregnancy test for women of child-bearing potential
- Review of viral studies: hepatitis serology (Hepatitis B surface antigen and antibody and Hepatitis C antibody), HIV-1, 2
- Underlying disease assessment per American Society for Blood and Marrow Transplantation/Center for International Blood and Marrow Transplant Research (ASBMT/CIBMTR) disease classification (Appendix E)
- BM biopsy and aspiration with FLT3 mutation testing via PCR
- TTE or MUGA scan
- Central line placement: peripherally inserted central line (PICC) or port

CONFIDENTIAL

STUDY DRUG: QUIZARTINIB
PROTOCOL DATE: 10 AUGUST 2020

DEVELOPMENT INNOVATIONS STUDY NUMBER: AML 48
VERSION 4.0

- Baseline signs and symptoms

